### 10.3 Laboratory Data

The clinical laboratory tests defined in the protocol (e.g., hematology, clinical chemistry and urinalysis) will be summarized.

Each laboratory variable will be summarized for all time points (starting with Baseline) with the number of non-missing observations, mean and standard deviation, median, Q1, Q3, minimum and maximum. Mean change from baseline to each applicable post-baseline visit will be summarized with the number of observations, baseline mean, and visit mean. The change from baseline mean, standard error will be presented for the mean change from baseline within each treatment group. In addition, descriptive statistics for values and changes from the baseline values in conventional units at each assessment time point will be presented for selected clinical laboratory parameters listed in [Appendix E](#). A description of reporting the lab values in conventional units in patient narratives (along with the standard reporting in SI units) is presented at the end of [Appendix E](#).

Changes in laboratory parameters will be tabulated using shift tables categorized as low, normal, or high based on the normal ranges of the laboratory used for each sample. A shift table will be provided to summarize shifts from baseline to the final post-baseline value.

Laboratory abnormalities will be evaluated based on potentially clinically significant (PCS) criteria ([Table 15](#)). For each laboratory PCS criterion, the number and percentage

of participants who have a laboratory value meeting the criteria will be summarized. Listings will be provided to summarize subject-level laboratory data for participants meeting PCS criteria. A listing of all AEs for participants with PCS Lab values will be provided.

In addition, ALT, AST, alkaline phosphatase, and total bilirubin will be categorized in [Table 16](#). The number and percentage of participants meeting each of the criteria for postbaseline hepatic laboratory abnormalities listed in [Table 16](#) will be summarized. The percentages will be calculated relative to the number of participants with at least 1 available postbaseline assessment. The numerator will be the total number of participants having at least 1 postbaseline value that meets the specific category during the study. A supportive listing will also be provided.

The number and percentage of participants with an adjudicated case (i.e.,  $ALT \geq 3 \times ULN$  and/or  $AST \geq 3 \times ULN$ ) will be summarized by treatment group and by relationship of ALT or AST elevation to study medication. The percentages will be calculated relative to the number of participants with at least 1 adjudicated case. The numerator will be the number of participants with at least 1 adjudicated case in the specific category of relationship. If a participant has more than 1 adjudicated case, he or she will be counted in the most relevant category of relationship.

Participants with an adjudicated case (i.e.,  $ALT \geq 3 \times ULN$  or  $AST \geq 3 \times ULN$ ) will be listed with their ALT and AST assessments, adjudication dates, relationship of ALT or AST elevation to study medication, and confounding factor(s). Additional listings will be provided for participants who meet  $ALT \geq 3 \times ULN$  or  $AST \geq 3 \times ULN$  and/or potential Hy's law and have one of the following categories: at least 1 abnormal liver biochemistry risk factor, at least 1 liver disease sign and symptom, at least 1 liver diagnostic test performed, consultation with a specialist for liver evaluation, liver lab tests performed, and drug screen performed, respectively.

A listing of possible Hy's Law cases, defined as those who meet all of the following conditions simultaneously, will be provided:  $ALT \geq 3 \times ULN$  or  $AST \geq 3 \times ULN$  that is associated with an increase in bilirubin  $\geq 2 \times ULN$  and alkaline phosphatase  $< 2 \times ULN$ .

A listing of urine pregnancy test results will be provided for female participants of child-bearing potential with at least one positive result.

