- ^b Effort should be made by site to not schedule Visit 7 earlier than 12 weeks after Day 1 (Day 84) to ensure that participants complete the full 12 weeks of treatment and have eDiary data through Day 84.
- ^c All participants who take at least 1 dose of study intervention must complete the safety follow-up period, except participants rolling over into Study 3101-312-002 (long-term safety extension study). For these rollover participants the Follow-up Visit will be performed at the end of the long-term safety extension study
- ^d Vital sign measurements: height, weight, sitting and standing pulse rate, respiratory rate, sitting and standing systolic and diastolic blood pressure, and body temperature. Height will be measured only at Visit 1.
- ^e For females of childbearing potential only, urine pregnancy tests will be performed.
- ^f Clinical laboratory determinations include chemistry, hematology, coagulation parameters (INR), and urinalysis to be collected for all study visits. Samples for serology and the urine drug screen will be collected only at screening (Visit 1).
- ^g PK sample should be collected prior to the first dose at Visit 2, 1 sample should be collected prior to the daily dose taken during one of the Visits 3 to 6, and the remaining samples should be collected 1 to 10 hours post the daily dose.
- ^h Participant should begin using the eDiary as soon as it is dispensed. If it is subsequently determined that the participant has failed entry criteria, the eDiary should be returned to site.
- ⁱ Participants should bring eDiary to visits and review with coordinators.
- ^j Data to be captured in the eDiary on a daily basis
- ^k At Visit 1, the *Screening/Baseline* assessment of the C-SSRS will be completed. At all other study visits, the *Since the Last Visit* C-SSRS will be completed.
- ^l Clinicians will complete the C-SSRS on eTablet.
- ^m PRO measures should be administered prior to any tests and/or evaluations unless indicated otherwise in the protocol (eg, during randomization visit, some tests will be conducted prior to PROs for eligibility).

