4.1. Overall Design

This is a global, multicenter, randomized, double-blind, placebo-controlled, parallel group study conducted at approximately 125 sites globally (North America, Europe and Asia/Pacific). Approximately 300 participants will be randomized to one of 2 treatment arms (placebo, and atogepant 60 mg QD) in a 1:1 ratio as follows:

- Placebo (n = 150)
- Atogepant 60 mg QD (n = 150)

Randomization will be stratified based on region (North America, Europe and Asia/Pacific), number of migraine days during the screening/baseline period (4 to < 8 and \geq 8) and number of classes of failed prior prophylactic treatments (2 and > 2).

Block randomization will be applied with a block size of 4 (2 treatment arms \times 2).

A randomization cap of 20% will be instituted to ensure that the planned randomized participants include no more than 20% of participants with 4 to < 8 migraine days at baseline.

Approximately 50% of randomized participants will have failed > 2 classes of prior prophylactic treatments.

Participation will begin with a 4-week screening/baseline period. Participants who complete the 4-week screening/baseline period and meet all entry criteria will be randomized to the double-blind treatment period of the study at Visit 2 (Randomization Visit). The double-blind treatment period will last 12 weeks, with a subsequent safety follow-up period of 4 additional weeks. Total duration of study participation for one participant is approximately 20 weeks.

There will be 8 scheduled clinic visits: Visit 1 (Screening/Baseline Visit), Visit 2 (Randomization Visit), Visit 3 (Week 2), Visit 4 (Week 4), Visit 5 (Week 6), Visit 6 (Week 8), Visit 7/ET (Week 12), and Visit 8 (Week 16/EOS/Safety Follow-up). The Visit 8/EOS/safety follow-up period must be completed for all participants who take at least one dose of study intervention, except for participants rolling over into Study 3101-312-002 (long-term safety extension study). For these rollover participants Visit 8 is not required, because the final Follow-up Visit will be performed at the end of the long-term safety extension study. For participants who screen fail for the long-term safety extension study, the Follow-up Visit of Study 3101-304-002 must be completed. (Please refer to the SoA, Section 1.3).

This study is conducted at US (IND) sites and non-US (non-IND) sites. Data from IND and non-IND study sites will be pooled together for analysis.

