The participant may be rechallenged with study intervention only after consultation with the sponsor's Medical Monitor. For participants who are not rechallenged with study intervention, they should be discontinued from the study and complete an ET Visit (Visit 7/ET assessments) and 4-week Follow-up Visit. Participants should receive appropriate follow-up as per SoC.

The investigator must contact the sponsor's Medical Monitor to discuss all cases of confirmed ALT/AST elevation $\geq 3 \times$ ULN. All ALT/AST elevations must be followed until ALT and AST return to $< 1.5 \times$ ULN and there is full clinical resolution.

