10.8.4. Visit 7/Early Termination (Week 12)

- Effort should be made by the site to not schedule Visit 7 earlier than 12 weeks after Day 1 to ensure participants complete the full 12 weeks of treatment and have eDiary data through Day 83. Prior to any other test or evaluations, administer PRO measures, including: HIT-6, PGIC, PGI-S, WPAI:MIGRAINE, PSSM, MIDAS, MSQ v2.1, PROMIS-PI and PHQ-9.
- Review eDiary data and compliance.
- Complete Healthcare Resource Utilization Questionnaire
- Collect eDiary, only from participants who completed the double-blind treatment period (Visit 2 to Visit 7/ET; for participants who discontinue study, eDiary collection will occur at Visit 8)
- Perform physical examination.
- Perform urine pregnancy test for women of childbearing potential.
- Collect vital sign measurements (weight, pulse rate, respiratory rate, blood pressure, and body temperature).
- Assess C-SSRS on eTablet (the “Since Last Visit” assessment of the C-SSRS will be completed).
- Perform and transmit ECG.
- Update concomitant medications and procedures.
- Review and assess AEs.
- Collect blood and urine samples for chemistry, hematology, INR, and urinalysis.
- Collect post-dose PK sample (for participants who consented). The PK sample should be collected 1 to 10 hours post the daily dose.
- Collect previous visit study intervention, review participant compliance, and perform accountability.
- Access IWRS and enter accountability.
- Advise participants who early terminated from the double-blind treatment period to continue completing their eDiary through the Follow-up Visit. Remind participant to bring eDiary to next visit.

10.8.5. Visit 8 (End of Study) Week 16

- Prior to any other test or evaluations, administer PRO measures, including: EQ-5D-5L, HIT-6, and MSQ v2.1.
- Collect eDiary from participants who early terminated from the double-blind treatment period, review eDiary data and compliance.
- Perform physical examination.
- Assess C-SSRS on eTablet (the “Since Last Visit” assessment of the C-SSRS will be completed).
- Collect vital sign measurements (weight, pulse rate, respiratory rate, blood pressure, and body temperature).
- Perform urine pregnancy test for women of childbearing potential.
- Collect blood and urine samples for chemistry, hematology, INR, and urinalysis.
- Update concomitant medications and procedures.
- Review and assess AEs.
- Access IWRS to enter study visit.

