## **10.5 Other Safety Analyses**

### **10.5.1 Electrocardiogram**

Descriptive statistics for ECG parameters (i.e., heart rate, PR interval, QRS interval, RR interval, QT interval, and QTc interval) at baseline, postbaseline, and changes from baseline values at each postbaseline timepoint will be presented by treatment group.

ECG parameter values are considered PCS if ECG values meet either the actual value or change from baseline PCS high criteria listed in [Table 18](#). The number and percentage of participants with PCS postbaseline values will be tabulated by study treatment. The percentages will be calculated relative to the number of participants with an available non-PCS baseline value and at least 1 postbaseline assessment. The numerator will be the total number of participants with an available non-PCS baseline value and at least 1 PCS postbaseline ECG value during the study. A supportive listing of participants with PCS postbaseline values will be provided. A listing of all AEs for participants with PCS ECG values will also be provided.

To evaluate ECG postbaseline values of clinical interest, the number and percentage of participants with post-treatment QTcF  $> 450$  msec,  $> 480$  msec, and  $> 500$  msec will be tabulated by treatment group.

The number and percentage of participants with an increase  $> 30$  msec but  $\leq 60$  msec, and with an increase  $> 60$  msec in QTcF will be tabulated. Participants will be counted only once for the most severe category. A supportive listing of participants with postbaseline QTcF increases  $> 30$  msec will be provided, including the PID number, study center, and all QTc values (including changes from baseline). A listing of all AEs for participants with postbaseline QTcF increases  $> 30$  msec will also be provided.

A shift table from baseline to the end of double-blind treatment period in the investigator's overall interpretation of the ECG will be presented by treatment group for the following categories: normal; abnormal, not clinically significant; abnormal, clinically significant.

A tabular display of participants with postbaseline clinically significant ECG abnormalities according to the investigator's overall interpretation will be provided.

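### SAP 10.3 ends the laboratory shift table at an unrestricted last value, so it mixes on-drug and off-drug samples and understates reversible changes in that table

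*SAP*

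**What the plan says.** SAP 10.3 classifies laboratory values as low, normal or high and fixes the end of the shift as follows: "A shift table will be provided to summarize shifts from baseline to the final post-baseline value". The SAP does not define the term further or tie it to a treatment period.

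On sampling, a footnote to the Protocol 1.3 schedule reads: "Clinical laboratory determinations include chemistry, hematology, coagulation parameters (INR), and urinalysis to be collected for all study visits". The Visit 7/ET and Visit 8 procedure lists (Protocol 10.8.4 and 10.8.5) both carry the instruction "Collect blood and urine samples for chemistry, hematology, INR, and urinalysis".

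On attendance, Protocol 4.1 says the Visit 8 follow-up "must be completed for all participants who take at least one dose of study intervention, except for participants rolling over into Study 3101-312-002". It adds: "For these rollover participants Visit 8 is not required". Protocol Section 7 also brings early terminators to Visit 8, 4 weeks after their last dose.

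**The concern.** A shift table for a safety laboratory parameter is normally read as showing what happened on the drug. Here one column pools two exposure states. Which state a participant contributes depends on whether he or she enters the extension, a choice made after randomisation that tolerability may influence. If atogepant moves an analyte out of range and the change resolves after stopping, the off-drug values pull the atogepant column toward placebo.

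The gap matters most where no other categorical display covers it. Values that leave the normal range without reaching the PCS limits of SAP Table 15 are counted only in the shift table, apart from the four hepatic parameters in Table 16. Those limits can be wide: creatinine above 1.5 × ULN, creatine kinase above 2.0 × ULN, platelets below 0.5 × LLN, neutrophils below 0.7 × LLN.

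**Working it through.** The plan gives no figure on this point to reproduce. The check traces the schedule and then sizes the dilution with a simple mixture.

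**Step 1. Which sample is the final one?**

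| Participant | Last scheduled laboratory sample in this study | Drug status | Source |
|---|---|---|---|
| Completer who rolls over | Visit 7 | On drug | Protocol 4.1 |
| Completer who does not roll over, with a Visit 8 draw | Visit 8 | About 4 weeks off | Protocol 4.1, 6.1.3, 10.8.5 |
| Early terminator with a Visit 8 draw | Visit 8 | 4 weeks off | Protocol Section 7 |
| Non-rollover with a remote or missed Visit 8 | Visit 7/ET or earlier | On drug or soon after stopping | Protocol Appendix 11, Table 10-3 (no laboratory row) |

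Two passages support the on/off labels. Protocol 8.5.1 times the Visit 7 pharmacokinetic sample at 1 to 10 hours after the daily dose, so completers are still dosing. Protocol 8.4, on overdose, puts loss of detectable drug on a scale of days (at least 2), against 4 weeks to Visit 8.

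**Step 2. How much is lost?** Let q be the share of the atogepant arm with an off-drug final value, and p_on and p_off the shift rates on and off drug. Assume the effect fully reverses by Visit 8 and that q is unrelated to who is affected. Placebo shows p_off at either visit.

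- Observed atogepant rate = (1 − q) × p_on + q × p_off
- Observed difference from placebo = (1 − q) × (p_on − p_off)

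The documents give neither q nor the shift rates. The table assumes p_off = 5% and p_on = 10% or 15%.

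| q | Share of excess retained | True excess 5 points | True excess 10 points |
|---|---|---|---|
| 0 | 100% | 5.0 | 10.0 |
| 0.10 | 90% | 4.5 | 9.0 |
| 0.15 | 85% | 4.25 | 8.5 |
| 0.25 | 75% | 3.75 | 7.5 |
| 0.40 | 60% | 3.0 | 6.0 |
| 0.50 | 50% | 2.5 | 5.0 |

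For example, at q = 0.15 and p_on = 10%: 0.85 × 10% + 0.15 × 5% = 9.25%, and 9.25% − 5% = 4.25 points. Per 150 participants, about 13.9 shifts are shown instead of 15.0, against 7.5 on placebo.

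The value 0.15 is borrowed from the dropout assumption in SAP 2.4: 0.15 × 150 = 22.5 per arm, if all of them had a Visit 8 draw. It is not a bound. Completers who do not roll over raise q; missed or remote Visit 8s lower it.

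**Step 3. What else shows on-treatment change?**

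- Descriptive values and mean changes by visit, with Visit 7 and Visit 8 separate (SAP 10.3).
- PCS counts and listings (SAP 10.3, Table 15).
- Hepatic categories counting any post-baseline value, from 1 × ULN upward (SAP Table 16).
- Adjudicated ALT/AST cases, the Hy's law listing and the summary of adverse events of special interest (SAP 10.3, 10.2.5).

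The by-visit summaries show no low/normal/high movement. For non-hepatic analytes, the shift table is the only planned categorical view between the normal limit and the PCS limit.

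**The case against.** The strongest reply is that this is one undefined phrase in one descriptive table, with several other outputs around it and no hypothesis test planned on it. That stands, and it limits the consequence to the shift table.

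The off-drug share may also be small. The rationale in the Amendment 2 summary of changes, for dropping Week 16 from the HIT-6 and MSQ endpoints, predicts that many participants will enter the extension and that few will have a Visit 8. That is not a rate, but it points to a small q. Table specifications sit in separate documents (SAP 1.0) and could restrict the value; the SAP text does not.

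Four stronger readings are tempting but not supported:

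- **That the ECG table shows the laboratory rule to be an oversight.** SAP 10.5.1 does specify "A shift table from baseline to the end of double-blind treatment period", but the schedule has ECGs only at Visits 1, 5 and 7 and none at Visit 8. That wording marks where scheduled ECGs stop. The period splits for newly emergent adverse events (SAP 10.2.1) and C-SSRS (SAP 10.5.2) are better precedents, although SAP safety reporting also runs into follow-up elsewhere.
- **That liver signals would be hidden.** Protocol 10.3.1 says "All ALT/AST elevations must be followed until ALT and AST return to" below 1.5 × ULN, so a final value may be a recovering one. It may still lie above the normal range, however, and the rise itself appears in the hepatic, adjudication and special-interest outputs.
- **That every non-rollover has an off-drug final value.** Loss to follow-up, a missed Visit 8 or a remote Visit 8 leaves an earlier value in place.
- **That ending the table at Visit 7/ET would be a complete repair.** The ET visit can come after dosing has stopped. Chemistry is generally repeated once or twice a week after a confirmed ALT/AST elevation, so a last-value rule can still pick up a recovered result.

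**Conclusion.** The point holds in a limited form. As written, SAP 10.3 pools on-drug and off-drug final values according to a choice made after randomisation, and the shift table understates a reversible effect by the off-drug share. At an assumed 15% it keeps about 85% of a fully reversible excess; at 40% it would keep 60%, though the sponsor's expectation of few Visit 8 attendances argues against a share that large.

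These figures assume full reversal within 4 weeks and no link between being affected and having an off-drug final value. Slower reversal means less dilution. If affected participants are more likely to stop or to decline the extension, dilution is greater for them.

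A reader might infer that the laboratory safety picture as a whole would look falsely clean. The documents do not support that: by-visit, PCS, hepatic, adjudication and special-interest outputs still capture on-treatment changes. What remains is a modest defect in one table, mainly for non-hepatic analytes that leave the normal range without reaching PCS limits. It is worth correcting because correction is cheap.

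**What to change.** In SAP 10.3, define the shift endpoint as the last non-missing value in the double-blind treatment period, taken no later than a stated short window after the last dose. The sponsor should state the window length.

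Optionally, add a shift from baseline to the worst on-treatment value. This would also catch changes that recover before the ET visit, which no last-value rule does reliably.

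Visit 8 values are already summarised by visit. No new summary is needed, beyond a separate off-treatment shift if wanted.

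The cost is one sentence in the SAP and one derived flag, with no new data. The small downside is that participants with no post-baseline laboratory value in the period and window drop out of the table, so their number should be shown.

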10.1.5.2. Hepatic Event Adjudication Committee

An Adjudication Charter will be established and will describe the process for the blinded surveillance, monitoring, and adjudication by the Clinical Adjudication Committee of events of post-treatment elevations of ALT and/or $AST = 3 \times ULN$ in the atogepant program. The purpose of this committee charter will be to provide a standardized process for the adjudication of data associated with these events in order to determine whether the elevation was related to atogepant.

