### **4.0 Analysis Populations**

The following population sets will be used for the analyses.

The Intent-to-Treat (ITT) Population includes all randomized participants.

The Safety Population includes all participants who received at least 1 dose of study intervention. All safety analyses will be performed using the Safety Population and based on the treatment actually received, regardless of assigned treatment according to the planned randomization. Participants will be summarized according to the study treatment received for the majority of treatment period.

The Modified Intent-to-Treat (mITT) Population includes all randomized participants who received at least 1 dose of study intervention, had an evaluable baseline period of eDiary data and had at least 1 evaluable post-baseline 4-week period (Weeks 1 to 4, 5 to 8, and 9 to 12) of eDiary data during the double-blind (DB) treatment period. All efficacy analyses described will be performed using the mITT population unless specified otherwise and based on the randomization assignment, regardless of the actual treatment received.

The Off-treatment Hypothetical Estimand Population includes all randomized participants who received at least 1 dose of study treatment, had an evaluable baseline period of eDiary data and had at least 1 evaluable post-baseline 4-week period (Weeks 1 to 4, 5 to 8, 9 to 12) of eDiary data during the DB treatment period and follow-up period, regardless of whether on study treatment or off study treatment. This population is used for the primary estimand in the support of the European submissions.

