**Table 16. Criteria for Hepatic Laboratory Abnormalities**

Laboratory Parameter	Categories
ALT	≥ 1 × ULN
	≥ 1.5 × ULN
	≥ 2 × ULN
	≥ 3 × ULN
	≥ 5 × ULN
	≥ 10 × ULN
	≥ 20 × ULN

Laboratory Parameter	Categories
AST	$\geq 1 \times \text{ULN}$
	$\geq 1.5 \times \text{ULN}$
	$\geq 2 \times \text{ULN}$
	$\geq 3 \times \text{ULN}$
	$\geq 5 \times \text{ULN}$
	$\geq 10 \times \text{ULN}$
	$\geq 20 \times \text{ULN}$
ALT or AST	$\geq 1 \times \text{ULN}$
	$\geq 1.5 \times \text{ULN}$
	$\geq 2 \times \text{ULN}$
	$\geq 3 \times \text{ULN}$
	$\geq 5 \times \text{ULN}$
	$\geq 10 \times \text{ULN}$
	$\geq 20 \times \text{ULN}$
Bilirubin Total	$\geq 1 \times \text{ULN}$
	$\geq 1.5 \times \text{ULN}$
	$\geq 2 \times \text{ULN}$
	$\geq 3 \times \text{ULN}$
	$\geq 5 \times \text{ULN}$
	$\geq 10 \times \text{ULN}$
	$\geq 20 \times \text{ULN}$
Alkaline Phosphatase	$\geq 1 \times \text{ULN}$
	$\geq 1.5 \times \text{ULN}$
	$\geq 2 \times \text{ULN}$
	$\geq 3 \times \text{ULN}$
	$\geq 5 \times \text{ULN}$
	$\geq 10 \times \text{ULN}$
	$\geq 20 \times \text{ULN}$

Laboratory Parameter	Categories
Concurrent Elevations 	ALT or AST $\geq 3 \times$ ULN and Bilirubin Total $\geq 1.5 \times$ ULN
	ALT or AST $\geq 3 \times$ ULN and Bilirubin Total $\geq 2 \times$ ULN
Potential Hy's Law 	ALT or AST $\geq 3 \times$ ULN and Bilirubin Total $\geq 2 \times$ ULN and ALP $< 2 \times$ ULN

ALT = alanine aminotransferase; AST = aspartate aminotransferase; TBL = total bilirubin; ALP = alkaline phosphatase; ULN = upper limit of normal (value provided by the laboratory).

1. Elevations are from the same day

**Vital sign** values will be considered PCS if they meet both the observed value criterion and the change from baseline value criterion, if both criteria are available, or meet either the observed value criterion or the change from baseline value criterion that is detailed in the following table.

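### The adjudicated liver-case table takes cases as its denominator, so no specified output gives committee-adjudicated drug-related elevations as a percentage of participants exposed or assessed

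*SAP*

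**What the plan says.** Protocol 10.1.5.2 sets up a blinded committee to adjudicate post-treatment ALT or AST elevations, "in order to determine whether the elevation was related to atogepant". SAP 10.3 describes how its findings are tabulated. Participants with an adjudicated case, meaning ALT and/or AST of at least 3 x ULN, "will be summarized by treatment group and by relationship of ALT or AST elevation to study medication", as a number and a percentage. The denominator is then fixed: "The percentages will be calculated relative to the number of participants with at least 1 adjudicated case". So is the numerator: "The numerator will be the number of participants with at least 1 adjudicated case in the specific category of relationship". For a participant with several cases, "he or she will be counted in the most relevant category of relationship". The SAP does not say whether the case denominator is taken within each arm or over both arms.

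The paragraph before it in SAP 10.3 covers the unadjudicated hepatic laboratory categories of Table 16, "Criteria for Hepatic Laboratory Abnormalities". There the rule is: "The percentages will be calculated relative to the number of participants with at least 1 available postbaseline assessment". Table 16 has a row for ALT or AST of at least 3 x ULN, the same laboratory threshold that defines an adjudicated case.

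**The concern.** The opening of the paragraph promises a by-arm percentage of participants with an adjudicated case, and the stated denominator cannot deliver it. Dividing by participants who already had a case gives the split of causality categories among cases. Having a case is a post-randomisation outcome that treatment may change, so the by-arm percentages no longer compare randomised groups. With the few cases to be expected they also rest on very small denominators.

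At stake is the one quantity the committee exists to supply. Table 16 carries no causality. The adverse event table by relationship in SAP 10.2.3 uses the investigator's assessment. SAP 10.2.5 says only that adverse events of special interest, which include ALT or AST of at least 3 x ULN, will be summarised and listed. No specified output gives the percentage of exposed or assessed participants whose elevation the committee judged related to study drug.

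**Working it through.** The documents state no figure for this table and no expected case rates, so there is no plan figure to reproduce. The only input taken from the plan is the arm size of 150 (SAP 2.3). Case counts, case rates and shares judged related are assumptions. Planned arm size stands in for the number exposed.

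**1. Any-case row.** If c is the number of participants with a case in an arm, the stated rule read per arm gives c/c = 100% when c is at least 1, and 0/0 when c = 0. This needs no assumption about counts.

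**2. Related row, illustration (counts assumed).** Atogepant has 4 cases, 2 related; placebo has 1 case, 1 related.

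| Percentage | Atogepant | Placebo |
|---|---|---|
| Related, SAP rule per arm | 2/4 = 50% | 1/1 = 100% |
| Related, SAP rule pooled | 2/5 = 40% | 1/5 = 20% |
| Related, per 150 exposed | 2/150 = 1.33% | 1/150 = 0.67% |
| Any case, per 150 exposed | 4/150 = 2.67% | 1/150 = 0.67% |

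Per arm, the order of the arms is reversed. Pooled, it is kept, as it always is with equal arms, but the figure is still not a risk.

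**3. How many configurations reverse.** Take every combination of 1 to 6 cases per arm, with any number of them related, and keep those where the related counts differ between arms. There are 602. The per-arm SAP percentages strictly reverse the related-per-exposed order in 50 (50/602 = 8.3%) and tie in 40 (40/602 = 6.6%). This is an unweighted count, not a probability.

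**4. Probabilities under assumed rates.** Cases are binomial with 150 per arm, and related cases are binomial within cases. The probability that at least one arm has no case is 1 - [1 - (1 - pA)^150] x [1 - (1 - pP)^150]. For 2% against 1%: 0.98^150 = 0.0483 and 0.99^150 = 0.2215, so 1 - 0.9517 x 0.7785 = 0.259. The last two columns come from full enumeration.

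| Case rate, atogepant / placebo | Share related, atogepant / placebo | An arm has no case | Related % reverses related per exposed | Related % points against any-case count |
|---|---|---|---|---|
| 2% / 1% | 50% / 50% | 0.259 | 0.088 | 0.264 |
| 3% / 1% | 50% / 50% | 0.230 | 0.160 | 0.319 |
| 2% / 1% | 30% / 30% | 0.259 | 0.033 | 0.207 |
| 2% / 1% | 30% / 60% | 0.259 | 0.062 | 0.330 |
| 3% / 1% | 70% / 70% | 0.230 | 0.236 | 0.341 |
| 1% / 1% | 50% / 50% | 0.394 | 0.035 | 0.173 |

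Reversal of the related-per-exposed order runs from 0.03 to 0.24. An arm with no case, and so no percentage, runs from 0.23 to 0.39.

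**The case against.** The strongest reply is that the table is a breakdown of causality among cases and should be read after Table 16. Table 16 shows how many assessed participants reached 3 x ULN; the adjudication table shows how those cases were judged. This stands. A reader might infer that the plan as a whole can reverse the direction of the hepatic risk, or that the two tables cannot be read together. The documents support neither: the threshold is the same, the Table 16 denominator is assessed participants, and the two displays nest.

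Further points also stand. Counts are reported and every adjudicated case is listed with its relationship, so a reader can rebuild the percentage. No test depends on this table. Protocol 10.3.1 requires these elevations on the adverse event form, so an investigator-assessed relatedness percentage is planned through SAP 10.2.3. A pooled denominator would not reverse the order with equal arms, and the table shells, which SAP 1.0 places in separate documents, may settle that.

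These replies do not remove the mismatch between the percentage announced and the denominator stated, and none supplies the committee's verdict per participant exposed.

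Two other inferences should be resisted. The rule for several cases, "he or she will be counted in the most relevant category of relationship", does not show that a participant with one related and one unrelated elevation would be counted as unrelated; the wording is loose, and the likely intent is the strongest relationship. Nor do the documents say why the committee was set up. Protocol 2.2 reports ALT rises with an earlier oral CGRP antagonist and no hepatic signal for atogepant to date, but does not link either to the committee.

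**Conclusion.** The point holds in a limited form. The denominator rule in SAP 10.3 does not give the by-arm percentage that the same paragraph announces, and adjudicated drug-related elevations per exposed or assessed participant appear in no specified output. On the per-arm reading, the natural one for a by-arm table, the any-case percentage carries no information, and the related percentages may rank the arms wrongly. That misranking is a minority outcome, and its probability rests wholly on rates that the documents do not give. Hepatic incidence at 3 x ULN is correctly covered by Table 16, and no efficacy conclusion is touched. The change is worth making because it concerns an adverse event of special interest and has essentially no downside.

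**What to change.** In SAP 10.3, report n/N (%) by arm for any adjudicated case and for each relationship category. Take N as the Safety Population participants in that arm with at least 1 postbaseline ALT or AST assessment, matching the Table 16 rule. Keep the share among cases as a second column, labelled as such, with its denominator stated as per arm or pooled. As a minor clarification, count a participant with several cases under the strongest adjudicated relationship, in line with the highest-relationship rule in SAP 10.2 and 10.2.3. The cost is two phrases in SAP 10.3 and one table shell; no new data are needed.
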